6.4.5 Reportable Adverse Events

This is a high risk population in which numerous serious adverse events are expected. Indeed, all subjects will require mechanical ventilation, with >50% of subjects expected to require >50% FiO₂ and/or vasopressors during the first 24 h based on our prior data^{33,34} and expected mortality is 70-80%³⁵ as we are excluding non-comatose subjects. Thus numerous serious adverse events (SAE) are anticipated during the conduct of this study with a complete list provided below. In this context we define a SUAE as any SAE that occurs in the setting of MetHb > 10% which may thus be attributed to the study drug.

Expected SAE (with severity grade indicated)

- Non-central nervous system thrombosis, particularly in vessels accessed for endovascular devices, assessed as symptomatic venous or arterial thrombus documented radiographically or ultrasonographically. (Grade 3)
- Sepsis assessed as the presence of microbiologically proven, clinically proven, or suspected infection; presence of Systemic Inflammatory Response Syndrome (SIRS); and development of at least one organ dysfunction within the preceding 24 hours. Diagnosis of SIRS will require the fulfillment of at least two of the following criteria (Grade 4):
 - Hyperthermia ($\geq 38^{\circ}\text{C}$) (which will only be evident after active temperature control);
 - Tachycardia ($\geq 90 \text{ bpm}$);
 - Tachypnea ($\geq 20 \text{ breaths/min}$) or an arterial pCO₂ $\leq 4.3 \text{ kPa}$ (32 mmHg) or mechanical ventilation;
 - White blood cell count $\geq 12,000/\mu\text{L}$ or $\leq 4,000/\mu\text{L}$ or left shift in differential white blood cell count $\geq 10\%$.
- Expected organ dysfunctions after OHCA (which may accompany SIRS in sepsis as defined above or separately) will be defined as:
 - Acute encephalopathy not explained by psychotropic medication (or attributable to the cardiac arrest) [Grade 3];
 - Thrombocytopenia $\leq 100,000/\mu\text{L}$ or drop in platelet count $> 30\%$ within 24 hours not explained by hemorrhage (Grade 3);
 - Arterial hypoxemia with an arterial pO₂ $< 8 \text{ kPa}$ (60 mmHg) when breathing room air or an oxygenation index (paO₂/FiO₂ $\leq 200 \text{ mmHg}$) not explained by presence of a pulmonary or cardiac disease (Grade 4);
 - Arterial hypotension with a systolic blood pressure $\leq 90 \text{ mmHg}$ or mean arterial blood pressure $\leq 65 \text{ mmHg}$ for at least one hour despite adequate fluid loading not explained by other causes of shock (Grade 4);

- Renal dysfunction with urine output ≤ 0.5 mL/kg/h for at least one hour despite adequate fluid loading or serum creatinine above 200 $\mu\text{mol/L}$ (2.3 mg/dL) [Grade 3];
 - Metabolic acidosis with base deficit ≥ 5.0 mmol/L or serum lactate ≥ 1.5 fold above local reference range (2.4 mmol/L at UPMC) [Grade 3].
- Pneumonitis assessed as the presence of air bronchograms on any chest x-ray within one week of the index cardiac arrest. (Grade 3)
- Since many of these comatose OHCA subjects will receive therapeutic hypothermia, anticipated SAE include:
 - Electrolyte abnormalities: defined as the presence of any of the following from induction of hypothermia until 72 hours (all Grade 3):
 - Hypokalemia assessed as serum potassium concentration < 3.5 mmol/L.
 - Hyperglycemia assessed as serum glucose > 240 mg/dL.
 - Hypophosphatemia assessed as serum phosphate concentration < 0.8 mmol/L.
 - Hypocalcemia assessed as serum ionized calcium < 2.2 mmol/L.
 - Bleeding (overt bleeding with Hb drop > 3 g/dL or transfusion; cardiac tamponade; bleeding requiring surgical intervention for control or intravenous vasoactive agents; intracranial hemorrhage; intraocular bleed compromising vision; operation for vascular closure for the purpose of controlling bleeding; fatal bleeding) [Grade 3]
 - Thrombosis (Grade 3)
 - Infection (Grade 3)
 - Fluid shifts defined as net fluid intake/output exceeding 3 L positive or negative in a 24h period (Grade 3)
- Pulmonary Edema: We shall monitor the incidence of pulmonary edema in each treatment duration group and assess whether there is a significant difference between groups. It will be defined as the presence of congestive heart failure on a hospital-based chest x-ray (first emergency department or ICU chest x-ray). OHCA is more common in patients with cardiomegaly, and this radiographic sign alone will not be a criterion for diagnosis of acute heart failure. (Grade 3)
- Other common post-OHCA SAE (Grade 3 unless specified) include pneumonia, cerebral bleeding, stroke, seizures, bleeding requiring transfusion or surgical intervention, rearrest (Grade 5), rib fractures, sternal fractures, internal thoracic or abdominal injuries as well as any other major medical or surgical outcomes will be recorded as noted in the hospital discharge summary.

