***Methemoglobin to be collected at 6 hours only**

DAY 1-3 (0-72 h post-ROSC) DATA

During post-ROSC days 1-3, the following data elements will be collected by a physician coinvestigator/research assistant prospectively or by a research assistant retrospectively. Refer to chart for visual of when labs will be drawn.

- Plasma labs measured variably between 24 and 72 h (troponin, arterial blood gas, lactate, plasma nitrite level, neuron specific enolase, ascorbate, cardiolipin, plasma banking)
- Urine labs measured variably between 24 and 72 h (renal failure and nitrated fatty acid measurements)
- *Full Outline of UnResponsiveness (FOUR) Score (components below)
- Eyes
- Motor
- Brainstem
- Reflex
- *Glasgow Coma Score (GCS)
- Eyes
- Verbal
- Motor
- EEG interpretation
- Dominant background present
- Reactivity present
- Seizures present
- Seizure type
- Burst-suppression ratio
- Estimate of survival to hospital DC
- Median nerve SSEP
- Witnessed aspiration
- New suspected infection last 24h
- Infection type
- Sputum color
- Vent mode
- Set Vt
- Set PC
- PEEP
- FiO2 (Use % oxygen)
- Peak Pressure
- Plateau Pressure
- CXR last 24h read may be pneumonia
- Positive airway culture last 24h

- Vital Signs (VS) (highest and lowest for each)
- Time to follow commands (assigned once)
- SOFA (worst in prior 24h period; some components may be missing)
- Respiratory (when no PaO₂ is available for PaO₂:FiO₂ ratio, use SpO₂:FiO₂ ratio)
- Nervous (based on GCS below)
- Cardiovascular
- Liver
- Coagulation
- Renal
- Interventions
- Coronary angiography
- PCI
- ECMO
- CPR
- CABG
- Mechanical ventilation hours
- NIPPV hours
- 24h FiO₂ AUC
- Tracheostomy
- Medications (dichotomous for use not dose)
- Alteplase
- Anti-epileptic
- Midazolam infusion
- Intermittent Benzodiazapine
- Propofol infusion
- Intermittent Propofol
- Opiate infusion
- Intermittent opiate
- Neuromuscular blockade infusion
- Intermittent neuromuscular blockade
- Neurostimulants
- *Vasopressors
- *Inotropes
- Ketamine
- Steroids (hydrocortisone/methylprednisolone)
- Cumulative vasopressor index (CVI; worst in prior 24h period)
- *BUN (highest value in prior 24 h)
- *Creatinine (highest value in prior 24 h)
- Hb
- WBC
- platelets
- PT
- INR
- PTT
- Bilirubin
- AST

- ALT
- BNP
- SvO2 (%)
- venous PaO2
- venous PaCO2

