2.3.3. Dose Selection

A number of studies have reviewed the safety of iNO in adults primarily in the setting of acute respiratory distress syndrome (ARDS). A recent meta-analysis found improved oxygenation but also greater acute kidney injury (AKI) resulting from iNO use.²⁵ When this was examined by dose, AKI only resulted in those patients receiving higher cumulative doses of iNO (≥ 40 ppm for ≥ 48 h).²⁶ Our study will limit iNO to 20 ppm for 12h hence AKI is not expected though we will track BUN and creatinine on all subjects. A separate meta-analysis examining effects of iNO in

acute hypoxic respiratory failure in adults and children found no associated adverse events.²⁷ A study of iNO used in transport identified no adverse events associated with the drug.²⁸ Although iNO significantly increases methemoglobin (metHb) levels, the increase (0.3%) is clinically insignificant and not associated with toxicity²⁹ which is uncommon until levels of 20-30% (we will consider > 10% a significant and unexpected adverse event). The best predictor of significant metHb >4% (as < 0-3% is considered within normal range) is cumulative iNO dose of >2000 ppm * h.³⁰ In our study subjects will receive only 250 ppm * h. We will monitor methemoglobin as part of our study at 6h. Although iNO lowers pulmonary blood pressure it has not been linked to reduction in systemic arterial blood pressure. We will monitor blood pressure effects closely in our study given the inherent instability of cardiac arrest subjects.

Effects of iNO after cardiac arrest has been studied in 4 preclinical animal studies.⁸⁻¹¹ These published studies demonstrated benefit using iNO 40 ppm started within 2h of ROSC which is additive to therapeutic hypothermia⁸ as well as neuroprotection without temperature control.⁹ These animal models include mouse and pig models of asystole and ventricular fibrillation (VF). In addition iNO has been shown to protect in animal models of focal heart¹²⁻¹⁵ and brain¹⁶⁻¹⁹ injury. This is important since most of the mortality and morbidity after OHCA results from heart and brain injury.²⁰

Animal models of asphyxia²¹ and other focal brain ischemia reperfusion models demonstrate NO deficiency early in reperfusion lasting at least 6h and benefits from iNO.^{16,19}

Information from prior clinical trials of iNO are available by cross reference in the Mallinckrodt NDA 20-845 (letter authorizing cross reference is included with application).

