2.3.5. Breaking the Blind

The safety monitor can request unblinding in the case of any serious unanticipated adverse event (SUAE) based on clinical judgement and will unblind whenever there is a MetHb level > 10% associated with any adverse event. The safety monitor will review clinical data from the study consisting of VS, vasopressor and inotrope use, labs and outcomes, at least every 4 weeks. In the event of a SUAE, the safety monitor will review the record within 48 h breaking the blind to determine whether this is a drug associated SUAE.

The Data Safety Monitoring Board (DSMB) will meet prior to the commencement of the trial and every 6 months. All data will be reviewed at 12 months or 60 subjects for safety. The DSMB and safety monitor are authorized to unblind at any time during the conduct of the study if they have safety concerns. The investigators will remain blind up until the point that the DSMB decides to halt the trial or trial conclusion.

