2.5.4 Safety Analysis

Section 6.4.5 outlines all potential SAE's and defines a SUAE as any SAE that occurs in the setting of $\text{MetHb} > 10\%$ which may thus be attributed to the study drug. All listed safety outcomes will be tabulated and summarized using basic descriptive statistics and tested using small sample exact methods.

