6. POTENTIAL RISKS AND BENEFITS

6.1 POTENTIAL RISKS

6.1.1 Risk of Experimental Drug Intervention

The known adverse events due to iNO are reviewed in the package insert and in section 2.3.3 above. Extensive safety data is available from published studies of iNO in critically ill patients with up to 2 year follow up.¹⁻⁶ In these studies rare cases of MetHb or excess nitrogen dioxide [NO₂], an airway irritant, are reported. These cases occur at doses ≥ 40 ppm. The INOVent delivery system provides constant monitoring of NO₂ levels and we will monitor MetHb to avoid toxicity. iNO may cause rebound hypoxia after prolonged use but this generally requires over 24h of use. We plan a 1h wean off the study drug to minimize this risk. Other NO donors (not iNO) can reduce blood pressure but this has not been noted in human or animal studies of iNO at the doses we plan to use. Acute kidney injury (AKI) has been noted in some clinical trials of iNO but again only with higher doses than we propose to use. We will nonetheless monitor BUN and creatinine as markers of renal function. Patients receiving iNO may experience increasing capillary wedge pressure and worsening heart failure. We will monitor oxygen requirement (FiO₂) and saturation (SpO₂) hourly during study drug administration and the PI or a physician coI will be notified of an increase of $>20\%$ in the patients' oxygen delivery (mechanical ventilator FiO₂) or a drop of > 50 mm Hg or 25% reduction (whichever is lesser) in the PaO₂ if the patient is on FiO₂ > 0.80 . This data along with any change in chest X ray (generally obtained daily in these patients) and hemodynamics collected hourly and hourly fluid intake and output will also be reviewed for each patient by the safety monitor as described above (2.3.5).

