6.4.2 Data Safety Monitoring Plan

Data Monitoring Plan. The proposed study will use the FDA definition of adverse events (AE) and serious adverse events (SAE). Any SAE, which is unexpected and related to study intervention, will be reported immediately to the IRB and will be followed by an additional letter detailing the nature of the SAE. In the event that a participant either withdraws from the study or the investigators decide to discontinue a participant due to a SAE, the participant will be monitored by the co-PIs until (a) a resolution is reached (e.g., the problem has resolved or stabilized with no further change expected), (b) the SAE is determined to be clearly unrelated to the study intervention, or (c) the SAE results in death. Outcomes of SAEs will be regularly reported to the IRB and the sponsor. A summary of the SAEs that occurred during the previous year will be included in the annual progress report as well as in the annual IRB renewal.

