6.4.6 Adverse Events Reporting Timeline

All SUAE associated with the use of the study drug (ie in the setting of MetHb $> 10\%$ or discovered to be drug associated after unblinding by the safety monitor and considered potentially resulting from the study drug by the DSMB) will be reported to the IRB within 24 hours of discovery of the incident with subsequent follow-up submission of a detailed written report.

The FDA will be notified by telephone or facsimile transmission of a human SUAE no later than 7 calendar days after receiving the respective human adverse event information, followed by the

subsequent submission of a written IND Safety Report.

Serious and unexpected adverse events associated with the use of the study drug or procedures will be reported to the IRB with subsequent follow-up submission of a detailed written report in accordance with the respective policies and procedures of the IRB. Written IND Safety Reports will be submitted to the FDA as soon as possible and, in no event, later than 15 calendar days following the investigator-sponsor's receipt of the respective adverse event information.

A summary report of the findings will be prepared and submitted to the regulatory agencies.

6.4.7 Withdrawal of Subjects and Stopping Criteria:

Subjects withdrawn from the study due to concern for SAE will be followed for all clinical outcomes but no further lab or imaging data will be collected. These subjects will not be replaced within the study. Subjects will not be withdrawn after enrollment except if requested by the subject or surrogate after notification. In this event all data and specimens required for study outcomes obtained up to that time and clinical outcomes to DC will be retained.

Discontinuation of the Clinical Trial:

This study can be stopped only by the DSMB. In such a case we will complete collection of clinical outcomes in all enrolled subjects (up to 90 d after OHCA). Subjects will not be notified of early study termination.

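### Sections 2.5.4 and 6.4.5 make MetHb above 10% a required condition for a SUAE, in conflict with 2.3.3, 2.3.5, 6.4.2 and 6.4.6, so the mandatory 48 h unblinded review misses other hazards the protocol names

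*Combined protocol and SAP*

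**What the plan says.** Section 6.4.5 says the investigators "define a SUAE as any SAE that occurs in the setting of MetHb > 10" percent, on the ground that such an event may be attributed to study drug. Section 2.5.4 (Safety Analysis) carries the same rule: it "defines a SUAE as any SAE that occurs in the setting of" MetHb above 10%.

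Actions follow from the label. Under 2.3.5, "In the event of a SUAE, the safety monitor will review the record within 48 h breaking the blind"; 6.4.4 repeats this. Section 6.4.6 sets 24 hours to the IRB and 7 calendar days to the FDA for a SUAE.

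On the likely MetHb level, 2.3.3 cites an increase of 0.3% with inhaled nitric oxide (iNO) and gives 0-3% as the normal range. It names cumulative dose above 2000 ppm·h as the best predictor of MetHb above 4%, and adds: "In our study subjects will receive only 250 ppm * h". On sampling, a note in 2.2 reads "Methemoglobin to be collected at 6 hours only", and Table 1 agrees.

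On other hazards, 6.1.1 states: "Patients receiving iNO may experience increasing capillary wedge pressure and worsening heart failure". It also discusses acute kidney injury (AKI), rebound hypoxia after the drug is stopped, and airway irritation from nitrogen dioxide.

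**The concern.** A definition of a drug-attributable serious event should let any plausible drug harm reach unblinded review. The rule in 6.4.5 and 2.5.4 admits one mechanism only, methemoglobinemia, at a level the protocol does not expect to see. The protocol ties none of the other 6.1.1 hazards to a raised MetHb.

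Two things are at stake. First, a drug-related case of heart failure, AKI or hypoxia with normal MetHb would start neither the mandatory 48 h unblinded review nor the shortest reporting clocks. Subjects here are enrolled under exception from informed consent. Second, the SUAE count would probably be near zero whatever the drug does through other mechanisms, so a report of no SUAEs would say little about safety.

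The sections also disagree about what a SUAE is, so staff applying different sections to the same event could reach different answers.

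**Working it through.** **1. The definitions side by side**

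- 2.3.3: MetHb above 10% is itself a significant, unexpected adverse event.
- 2.3.5: SUAE stands for a serious unanticipated adverse event. The safety monitor may request unblinding on clinical judgement. Separately, unblinding is mandatory when MetHb above 10% accompanies any adverse event, serious or not.
- 2.5.4 and 6.4.5: an SAE together with MetHb above 10%.
- 6.4.2: "Any SAE, which is unexpected and related to study intervention, will be reported immediately to the IRB", with no MetHb condition.
- 6.4.6: MetHb above 10%, or "discovered to be drug associated after unblinding by the safety monitor and considered potentially resulting from the study drug by the DSMB". A separate 15-day FDA route covers serious, unexpected, drug-associated events with no MetHb condition.

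MetHb above 10% is thus the event itself (2.3.3), a separate trigger (2.3.5), a required condition (2.5.4, 6.4.5), one of two routes (6.4.6), or absent (6.4.2).

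**2. Exposure, reproducing the stated 250 ppm·h**

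Inputs from 2.3.4: 20 ppm for 12 h, then 10 min each at 10, 5, 4, 3, 2 and 1 ppm.

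- Main period: 20 × 12 = 240 ppm·h.
- Wean: (10+5+4+3+2+1) × 10/60 = 4.17 ppm·h.
- Total: 244.2 ppm·h, 2.3% below the stated 250, so the figure reproduces to rounding.
- Against the cited predictor of MetHb above 4%: 244.2/2000 = 12.2% (250/2000 = 12.5%). At 20 ppm, 2000 ppm·h would take 2000/20 = 100 h.

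**3. Distance to the trigger**

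Taking the 0.3% as percentage points, the top of the normal range plus the cited rise is 3 + 0.3 = 3.3%, which is 6.7 points short of 10%. This is an expected level, not a maximum.

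The documents give no probability of MetHb above 10%. With 65 iNO subjects (2.5.1) and an assumed per-subject risk p, the chance of at least one case is 1 − (1 − p)^65:

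| Assumed p | Chance of at least one |
|---|---|
| 0.01% | 0.6% |
| 0.1% | 6.3% |
| 0.5% | 27.8% |
| 1% | 48.0% |

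**4. The single sample**

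At 6 h, exposure is 20 × 6 = 120 ppm·h, and 120/244.2 = 49% of the total. The concentration at that time is the full 20 ppm; it is the cumulative exposure that is half complete. Of 13 dosing hours, 7 (54%) follow the sample. An SAE in those hours or after the wean has no scheduled concurrent MetHb value.

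**5. A test case: drug-related AKI with normal MetHb**

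- 6.4.5 and 2.5.4: not a SUAE.
- 6.4.2 and the 15-day route in 6.4.6: both require unexpectedness, but 6.4.5 lists renal dysfunction as expected. The same list weakens the word unanticipated in 2.3.5.
- Second SUAE route in 6.4.6: this needs prior unblinding, which is mandatory only for a SUAE or for MetHb above 10%. Otherwise it is discretionary.

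So no mandatory route leads to the 48 h review. The same reasoning applies to hypoxemia and pulmonary edema, which are also on the expected list.

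**The case against.** The strongest reply is that 2.3.5 already comes close to the right rule. It spells out SUAE as a clinically judged unanticipated event and treats MetHb above 10% as a separate trigger. Sections 6.4.2 and 6.4.6 report unexpected related events without reference to MetHb, and 2.3.5 lets the monitor and DSMB unblind at any time on safety concerns, so the second route in 6.4.6 is not fully circular. This stands, and it rules out reading MetHb as the only path to attribution anywhere in the protocol. It does not remove the conflict with 2.5.4 and 6.4.5.

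A reader might also infer that the trial cannot detect the other harms. The documents do not support that. Section 2.5.4 tests all listed safety outcomes with exact methods. Section 6.1.1 requires a physician to be notified of oxygenation deterioration and sends X-ray, hemodynamic and fluid data to the monitor. Review is at least every 4 weeks by the monitor (6.4.4) and every 6 months by the DSMB (6.4.2). Section 6.5.2 keeps a research assistant present during dosing and lets co-investigators stop drug. These routes are real, but none requires unblinded review within 48 h. The pulmonary edema comparison in 6.4.5 also rests on the first emergency department or ICU film, which may precede study drug.

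The protocol qualifies its hazards: it ties AKI to at least 40 ppm for at least 48 h, says rebound hypoxia generally needs over 24 h of use, and has nitrogen dioxide monitored continuously. These qualifiers lower the expected frequency but do not justify a definition that excludes the events. The heart failure warning carries no such qualifier.

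Finally, with expected mortality of 70-80%, attributing single cases is hard, and comparison between arms is a defensible main tool. That is fair, and nothing in the protocol makes the SUAE count its safety conclusion.

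**Conclusion.** The point holds as a gap in the SUAE-triggered review and as a contradiction between sections. It is not a failure of all safety oversight, and the primary endpoint and its analysis are unaffected. Severity: should fix.

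Under 6.4.5 and 2.5.4, the 48 h review and the 24 h and 7-day clocks depend on a level that the protocol's figures put far above expectation, measured once with 51% of cumulative exposure still to come. Events resembling the heart failure, AKI and rebound hypoxia hazards can miss both the MetHb test and the unexpectedness tests.

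That the trigger is remote is an inference from the protocol's rationale. The titles of references 29 and 30 show that the 0.3% and 2000 ppm·h figures come from infants and children, so carrying them to post-arrest adults is an assumption. The table of probabilities rests on assumed risks. It would be wrong to read 3.3% as a ceiling or to call MetHb above 10% impossible.

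**What to change.** Reconcile 2.3.3, 2.3.5, 2.5.4, 6.4.2, 6.4.5 and 6.4.6 to one SUAE definition: serious, unexpected in nature or severity, and suspected to be related to study drug. Make MetHb above 10% sufficient but not necessary. State that the list in 6.4.5 describes what cardiac arrest is expected to produce, so an SAE on it can still qualify when it is suspected to be drug related or is more severe than expected. Use this definition for the 48 h review and the reporting clocks.

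Reconcile the 6 h-only MetHb sampling with the cumulative-dose rationale in 2.3.3, and say how an SAE after 6 h is to be classified. Do not present the SUAE count as evidence of safety; rely on the between-arm comparison of listed outcomes.

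The cost is an amendment to wording and some added safety-monitor review. Requiring suspected relatedness limits that load. Routing every matching SAE would not be practical: 6.4.5 expects more than half of subjects to need over 50% inspired oxygen and/or vasopressors, and counts one hour of low urine output despite fluids as renal dysfunction.

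### The hypoxemia SAE drops events with a cardiac or pulmonary explanation, so it can lose the heart-failure events 6.1.1 warns of; the hypotension SAE has a similar, lesser filter

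*Combined protocol and SAP*

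**What the plan says.** Section 6.4.5 lists organ dysfunctions expected after OHCA and says they may accompany sepsis or occur separately. Two of them are filtered by cause:

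- Hypoxemia is a PaO2 below 60 mmHg on room air or a PaO2/FiO2 of 200 mmHg or less, and it counts only when "not explained by presence of a pulmonary or cardiac disease (Grade 4".
- Hypotension is a systolic pressure of 90 mmHg or less or a MAP of 65 mmHg or less, and it counts only when it persists "for at least one hour despite adequate fluid loading not explained by other causes of shock (Grade 4".

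No section says who decides whether an event is explained, or by what rule.

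Section 2.5.4 points to the 6.4.5 list and states: "All listed safety outcomes will be tabulated and summarized using basic descriptive statistics and tested using small sample exact methods". Section 2.5.2 makes all tests two-sided at 0.05.

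On expected harms, 6.1.1 says: "Patients receiving iNO may experience increasing capillary wedge pressure and worsening heart failure". It follows this with hourly checks of FiO2 and SpO2 and an alert based on FiO2 or PaO2. On blood pressure it says: "Other NO donors (not iNO) can reduce blood pressure but this has not been noted in human or animal studies of iNO" at the planned doses.

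Pulmonary edema is a separate SAE in 6.4.5: "We shall monitor the incidence of pulmonary edema in each treatment duration group and assess whether there is a significant difference between groups". The film that defines it is the "first emergency department or ICU chest x-ray".

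**The concern.** The two clauses suit a sepsis definition, where the aim is to attribute organ failure to infection. In a blinded, placebo-controlled trial the between-arm comparison needs no such attribution, because the placebo arm supplies the background rate.

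Here the filter is also aligned with the harm under watch. The protocol expects iNO harm to appear as worsening heart failure and looks for it through oxygenation. Hypoxemia that arises that way has a cardiac explanation and can be set aside. Every subject has just had a cardiac arrest, so such an explanation is nearly always at hand, and the count depends on judgement without a rule.

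At stake is the hypoxemia line in the SAE comparison. If the excess events on iNO are the ones most likely to be called cardiac, the observed difference shrinks toward zero. Blinding stops assessors from favouring an arm knowingly. It does not stop a cause filter from removing more events in the arm where that cause is more common.

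**Working it through.** **Reading the sections together**

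1. 6.1.1 gives the harm route: iNO, then raised wedge pressure and worsening heart failure, with oxygenation as the signal.
2. 6.4.5 counts hypoxemia only if neither pulmonary nor cardiac disease explains it. It covers organ dysfunction outside sepsis, so the filter is not confined to septic subjects.
3. 2.5.4 tests the outcomes as listed, so the filtered count is what the arms are compared on.
4. The item aimed at heart failure, pulmonary edema, is read on the first ED or ICU film. Section 2.2 says study drug is generally connected in the ED or ICU, and 2.3.3 says most subjects at the larger center arrive 1 to 3 h after ROSC. That film can precede exposure, in which case it describes baseline. The item also refers to treatment-duration groups, which a two-arm trial of one 12 h regimen does not have.

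**Illustration of size**

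The documents give no rate for these events and no share that would be filtered, so there is no stated figure to reproduce. From the documents: 65 per arm (2.5.1), two-sided 0.05 (2.5.2), exact test (2.5.4). Assumed:

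- c, the placebo rate of all threshold events: 20%, 30% or 40%
- e, the iNO excess: 20 points
- s, the share of background events filtered out: one half
- d, the share of the excess filtered out: none, half or all

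Counted rates are c(1 − s) on placebo and c(1 − s) + e(1 − d) on iNO. For c = 30% and d = one half: placebo 0.30 × 0.5 = 15%, iNO 0.15 + 0.20 × 0.5 = 25%.

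Power is the sum, over all pairs of event counts (a, b), of Bin(a; 65, p1) × Bin(b; 65, p2) for the pairs where Fisher's two-sided p is at or below 0.05.

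| c | Every event counted | Filter, d = 0 | Filter, d = 1/2 | Filter, d = 1 |
|---|---|---|---|---|
| 20% | 20 v 40: 64% | 10 v 30: 78% | 10 v 20: 28% | 10 v 10: 2.4% |
| 30% | 30 v 50: 59% | 15 v 35: 70% | 15 v 25: 23% | 15 v 15: 2.8% |
| 40% | 40 v 60: 54% | 20 v 40: 64% | 20 v 30: 20% | 20 v 20: 3.0% |

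The risk difference counted is 20 points with no filter, and 20, 10 and 0 points across the three filtered columns. The last column shows only the exact test's own false-positive rate.

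In the d = 1/2 column the same share is removed from both arms. At c = 30% the risk ratio stays at 50/30 = 25/15 = 1.67, so that column shows lost events and lost power, not differential filtering. Differential loss of the excess appears only when d exceeds s, as in the last column.

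**The case against.** A reader might infer that the cardiac harm attributed to iNO is left out of the safety comparison altogether, and that the DSMB would see clean tables. The documents do not support either reading.

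- Section 2.4 compares by arm, with no cause filter, blood gases at 0, 6, 12 and 24 h when available, MAP, vasopressor and inotrope need, cardiac output, LVEF and lactate. NYHA class III/IV at discharge is part of the primary composite.
- Within 6.4.5, the renal and the lactate/base-deficit items have no cardiac exclusion. Rearrest and other major outcomes are listed too.
- The DSMB reviews all data at 12 months or 60 subjects (2.3.5). The safety monitor sees vital signs, vasopressor and inotrope use, ventilator settings, fluid balance and labs at least every 4 weeks (6.4.4, 6.5.2).

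All of this stands. It does not repair the hypoxemia item. The section 2.4 endpoints do not count treatment-emergent hypoxemia by threshold, and case-by-case review is not a comparison of arms.

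It can also be said that the hypoxemia clause means established disease, not failure that emerges on treatment. That reading is possible, but the text does not state it, and the ambiguity is itself part of the problem.

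The hypotension half is weaker. Sections 2.3.3 and 6.1.1 say iNO has not been linked to systemic hypotension, and MAP and vasopressor need are compared anyway. Still, 2.3.3 promises close monitoring of blood pressure, and on a plain reading the clause drops cardiogenic shock.

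Finally, the filter need not hurt. If it removed only background events it would raise power, as the d = 0 column shows. And counting everything does not guarantee an informative test: at 30% versus 40%, exact power is only 18%.

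**Conclusion.** The point holds, at moderate severity. Followed to the letter, the hypoxemia definition can discard events that arise by the protocol's own named route of harm, and there is no rule to prevent it. The hypotension clause has the same form but less consequence. Pulmonary edema, as timed, does not reliably capture treatment-emergent heart failure, so it does not close the gap.

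The direction, toward no difference, depends on drug-related events being called cardiac at least as readily as background events. That is plausible from 6.1.1 but not shown by any figure in the documents. The size is unknown: at an assumed 30% versus 50%, exact power runs from 59% with every event counted to 23% with half filtered in both arms and 2.8% if the whole excess is filtered. These figures do not prove differential bias. The primary analysis and the data capture are unaffected, so this does not block the trial.

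**What to change.** For the 2.5.4 tabulation and the DSMB reports:

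- Count every hypoxemia and hypotension episode that meets the existing numeric thresholds of 6.4.5 with onset after study drug start, whatever its presumed cause.
- Use the 0 h values to identify subjects already past a threshold at baseline, and list them separately by arm.
- Record the assessor's attribution, made under blinding, in a separate descriptive column that does not decide whether the event counts.
- Report the risk difference with a 95% CI beside the exact p-value.

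A useful companion change is to define pulmonary edema over a stated window from study drug start, with the first film as baseline, and to replace the reference to duration groups with the two arms.

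The cost is mainly wording in 6.4.5 and 2.5.4. Vital signs and ventilator settings are already followed hourly during dosing, blood gases are scheduled at 0, 6 and 12 h, and chest films are generally daily. The downside is longer event lists in both arms, many of them background: 6.4.5 itself expects more than half of subjects to need more than 50% FiO2 and/or vasopressors in the first 24 h. PaO2/FiO2 can be judged only when a gas is drawn, so the same sampling times should be used in both arms.
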